4. STUDY DESIGN

This project will be a multi-site retrospective cohort analysis of trans-vaginally placed synthetic midurethral slings (MUS) implanted in patients for the indication of stress urinary incontinence for mid- and long-term outcomes (1 year and greater). We will identify all patients at each of the sites that have received a MUS through administrative and device implantation data. The key exposures will be MUS devices identified by administrative codes. Because ascertainment of the surgical approach is critical to the evaluation of post-operative complications, and has differing rates depending on the approach, we will determine which approach was used: Retropubic MUS (RPMUS), Transobturator MUS (TOMUS), Single-Incision Sling (SIMUS), or Adjustable Sling (AMUS). In prior work at Mayo, determination of the surgical approach was present in 100% of cases in the operative notes. We will also identify all patients that received a surgery for SUI without mesh (autologous or cadaveric fascial sling or burch colposuspension or bulking agents) and evaluate the same outcomes of interest in that population separately to provide an indirect comparison group. No direct comparison of mesh and non-mesh groups will be conducted. Patients with concomitant surgeries at the time of trans-vaginal mesh implantation for SUI will be included. The primary outcomes of interest are long-term safety outcomes relevant to these devices and defined in Section 7. In addition, using the Mayo Clinic data, we will be able to validate the electronic data with the manually curated data from 2010-2012². We will leverage this data to better understand how much of the data can be electronically generated and where additional information would need to be collected in an electronic environment.

Beyond the variables collected for exposures, outcomes, and cohort inclusion/exclusion, important covariates relevant to the device exposures and outcomes, and present prior to the surgery, will also be collected.

These include:

- Patient demographics
- Chronic pain
- Prior abdominal surgery
- Receipt of urodynamic testing (structured data will not have the results)
- BMI
- Insurance payer

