7. STUDY OUTCOMES

The primary outcomes of interest are:

- Re-operation (revision, incision, excision, removal) or mesh removal
- Chronic pain, defined as pain persisting at least three months after surgery⁴⁹
- Voiding symptoms, defined as recurrence of incontinence or new retention.

All outcomes are determined in the surveillance period after surgery. Re-operation or mesh removal is defined as a surgery for any kind of mid-urethral sling, urethral bulking agent, bladder neck pubovaginal sling (autologous or allograft), or revision for mesh exposure. Resumption of voiding symptoms was defined as subsequent urinary retention, urinary incontinence, and sling revision for urinary retention. Chronic pain is defined as a new post-operative pain score >3 of 10 on vital sign data occurring over at least 3 months or greater of duration, or diagnosis codes related to abdominal and pelvic pain.

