Covariate	Chronic Pain	Admin codes, also possibly pain medication. Chronic suprapubic pain Chronic pelvic, groin, or leg pain- ICD 9/10 625.9, 338.29, 789.09/R10.2, G89.29, R10.30 Chronic postprocedural pain- ICD 9/10 338.28/G89.28 Dyspareunia- ICD 9/10 625.0/N94.10, N94.12, N94.11, N94.19	Med & admin both structured	Yale Team: After reviewing the variable list, it seems as if the proposed variables are ascertainable. However, there will be some variables that will be more difficult to capture, for instance, the "post- procedural pain" variable will likely require going through free text and notes to determine if a pain score has been recorded.'
Covariate & Outcome	Voiding symptoms: urgency, obstructive symptoms, urinary retention, UTI	Admin codes Urinary Retention ICD9/10 for 596.0, 598.1, 598.2, 598.8, 598.9, 599.6, 599.69, 788.2, 788.21, 788.29, 788.61, 788.62, and 788.65. ²⁸ Urinary Tract Infection (UTI)- >100,000 CFU of bacteria on urine culture and symptoms of UTI Recurrent UTI (\geq 2 in 6 months or \geq 3 in 12 month) Urgency Urinary Incontinence ICD 9/10 (788.31/N39.41) Urinary Retention Requiring Prolonged Catheterization ICD 9/10 788.20/R33.9 and CPT 51701 or 51702 Overactive bladder (OAB)- ICD10 N32.81 or SNOMED 762262008 Urinary Tract Infection ICD 9 599.0 Infection of Kidney, NOS ICD 9 590.9 Urinary Tract Infection, site not specified ICD 10 N39.0 Urinary incontinence ICD 9: 625.6 Stress urinary incontinence, female 599.82 Intrinsic sphincter deficiency 788.30 Urinary incontinence, unspecified 788.31 Urge incontinence 788.33 Mixed incontinence (male) (female) 788.34 Incontinence without sensory awareness 788.35 Post-void dribbling		recurrence of incontinence or new retention. subsequent urinary retention, urinary incontinence, and sling revision for urinary retention Capture as date/time SME determined that this may be hard to separate from pre- existing condition

Protocol 1				[15 July 2020]
		788.36 Nocturnal enuresis		
		788.37 Continuous leakage		
		788.38 Overflow incontinence		
		788.39 Other urinary incontinence		
		ICD10:		
		N39.3 Stress incontinence (female) (male)		
		N36.42 Intrinsic sphincter deficiency (ISD)		
		R32 Unspecified urinary incontinence		
		N39.41 Urge incontinence		
		N39.46 Mixed incontinence		
		N39.42 Incontinence without sensory awareness		
		N39.43 Post-void dribbling		
		N39.44 Nocturnal enuresis		
		N39.45 Continuous leakage		
		N39.490 Overflow incontinence		

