		N39.498 Other specified urinary incontinence		
		Prolapse		
		ICD 9:		
		618.01 Cystocele, midline		
		618.02 Cystocele, lateral		
		618.03 Urethrocele		
		618.81 Incompetence or weakening of		
		pubocervical fascia		
		618.1 Uterine prolapse without mention of		
		vaginal wall prolapse		
		618.2 Uterovaginal prolapse, incomplete		
		618.3 Uterovaginal prolapse, complete		
		618.4 Uterovaginal prolapse, unspecified		
		618.5 Prolapse of vaginal vault after		
		hysterectomy		
		618.6 Vaginal enterocele, congenital or acquired		
		618.84 Cervical stump prolapse		
		618.04 Rectocele		
		618.05 Perineocele		
		618.82 Incompetence or weakening of		
		rectovaginal fascia		
		618.00 Unspecified prolapse of vaginal walls		
		618.09 Other prolapse of the vaginal walls		
		without mention of uterine prolapse		
		618.7 Old laceration of muscles of pelvic floor		
		618.83 Pelvic muscle wasting		
		618.89 Other specified genital prolapse		
		618.9 Unspecified genital prolapse		
		ICD-10 CM :		
		N81.0 Urethrocele		
		N81.10 Cystocele, unspecified		
		N81.11 Cystocele, midline		
		N81.12 Cystocele, lateral		
		N81.2 Incomplete uterovaginal prolapse		
		N81.3 Complete uterovaginal prolapse		
		N81.4 Uterovaginal prolapse, unspecified		
		N81.5 Vaginal enterocele		
		N81.5 Vaginal enterocele		
		N81.89 Other female genital prolapse		
		N99.3 Prolapse of vaginal vault after		
	1	1953.5 I TOTAPSE OF VAGITAL VAULT ALLEL	1	1
		hysterectomy		
		hysterectomy		
Exposure	SUI with Mesh	Admin Codes CPT 57288	Yes	Capture as date/time

Version 2.0 [15 July 2020]

Protocol 1				[15 July 2020]
Exposure	SUI without Mesh	Admin Codes	Yes	Capture as date/time
	IVIES11	CPT/ICD-9-CM/ICD-10-PCS 51715/ 59.72/3E0K3GC, 3E0K4GC Injection of implant into the urethra and/or bladder neck (collagen implant)		
		CPT/ICD-9-CM/ICD-10-PCS 51990, 51992/59.5/OTSD0ZZ, OTSD4ZZ Laparoscopic urethral suspension, laproscopic sling procedure		
		CPT/ ICD-9-CM/ICD-10-PCS 51841, 51840/ 59.5/0TSD0ZZ, 0TSD4ZZ Anterior vesicourethropexy, or urethropexy (eg, Marshall- Marchetti-Krantz, Burch)		
		CPT/ICD-9-CM/ICD-10-PCS 51845/59.5/0TSD0ZZ, 0TSD4ZZ Abdominovaginal vesical neck suspension		
		CPT /ICD-9-CM/ICD-10-PCS 57220/ 59.3/0TSC0ZZ, 0TSC4ZZ Kelly plication of urethrovesical		

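### The appendix row for the primary voiding-symptom outcome lists infection, overactive bladder and, as it reads, prolapse codes that Section 7 does not include, and marks none of them covariate-only

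*Protocol*

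**What the plan says.** Section 7 (Study Outcomes) lists among the primary outcomes "Voiding symptoms, defined as recurrence of incontinence or new retention". Later in the section it gives the working definition: "Resumption of voiding symptoms was defined as subsequent urinary retention, urinary incontinence, and sling revision for urinary retention". Infection, overactive bladder and prolapse are not mentioned.

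The matching row of the Data Collection table in Section 13 (Appendices) has the category Covariate & Outcome and the title "Voiding symptoms: urgency, obstructive symptoms, urinary retention, UTI". Its definition cell holds retention codes, a UTI definition based on culture plus symptoms, a recurrent-UTI threshold, urge incontinence, an overactive bladder code (N32.81), and then "Urinary Tract Infection ICD 9 599.0 Infection of Kidney, NOS ICD 9 590.9 Urinary Tract Infection, site not specified ICD 10 N39.0". A list of incontinence codes follows. After that, as the table reads, a list headed Prolapse begins with "618.01 Cystocele, midline" and runs through the ICD-9 618 codes and the ICD-10 N81 and N99.3 codes.

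The Notes column of the same row reads "recurrence of incontinence or new retention. subsequent urinary retention, urinary incontinence, and sling revision for urinary retention Capture as date/time", which is Section 7's definition again. It adds: "SME determined that this may be hard to separate from pre- existing condition".

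**The concern.** The appendix is where a primary outcome becomes a set of codes. Here the codes go beyond the outcome they are meant to capture. A urinary tract infection, a kidney infection, an overactive bladder diagnosis or a prolapse diagnosis is neither incontinence nor retention as Section 7 uses the terms.

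Section 6 has one site write the code that turns the common data model into the analytic file, so whichever list is used is used everywhere. Sections 4 and 9 then tabulate the outcome by site and, if the data allow, model it from surgery as a time to event. Section 3 says the FDA intends to add the results to its evidence on the risk of these procedures. If the full list were run, the reported voiding-symptom rate and the predictors chosen for it would partly describe infection and prolapse.

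**Working it through.** The protocol states no expected voiding-symptom rate, so there is no figure to reproduce. The check sets the two definitions side by side.

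| Component | Section 7 | Notes column of the row | Title or code list of the row |
|---|---|---|---|
| Urinary incontinence | yes | yes | yes (codes) |
| Urinary retention | yes | yes | yes (title and codes) |
| Sling revision for retention | yes | yes | no code in this row |
| UTI | no | no | yes (title; 599.0, N39.0; culture and recurrence definitions) |
| Kidney infection | no | no | yes (590.9) |
| Overactive bladder | no | no | yes (N32.81) |
| Pelvic organ prolapse | no | no | as read: 618 codes, N81 codes, N99.3; not in the title |

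Three points follow.

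1. **The row disagrees with Section 7 and with itself.** Its Notes column is narrow, and its title and code list are wide. Nothing assigns any code to the covariate role only.

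2. **The direction is fixed.** Let p be the proportion with a Section 7 event by a given time and q the proportion with one of the extra codes. The proportion with either lies between max(p, q) and p + q (at most 1), so it is never below p. For each woman the first-event time under the wide list is min(time to Section 7 event, time to extra code), so it is never later than under the narrow list.

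3. **The size is not available.** The documents give no q for UTI, kidney infection, overactive bladder or prolapse. The nearest figures for p are the voiding dysfunction rates in Section 1.1 (3-30% after retropubic and 0-16% after transobturator slings). Those describe a differently worded outcome and span a wide range, so they do not support an estimate.

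On prolapse, Section 5 excludes prior prolapse surgery but not a prolapse diagnosis, and Section 4 states: "Patients with concomitant surgeries at the time of trans-vaginal mesh implantation for SUI will be included". If some of that surgery is prolapse repair, which is an inference, prolapse codes could recur after the index date in women with no new voiding problem.

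**The case against.** The best defence is that the row serves two purposes. Its Notes column gives the outcome in Section 7's terms, so the wider list can be read as the covariate list. The table is also plainly a working inventory, with open questions left in several cells. That reading is possible and may be the intended one, but the protocol does not state it, and a title that names UTI in a row labelled as an outcome points the other way.

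Chart review of 50 to 100 cases per site, covering outcomes among other elements, could expose miscoding. It checks codes against charts, however, and cannot decide which definition is meant.

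The objection is strongest on prolapse. The block has its own subheading, is not in the row title, and follows nearly the same order as the example diagnosis list at the end of the appendix. It may have been copied across, or a row break may have been lost in converting the table. A reader might infer that any rectocele noted after surgery becomes an event, but the text does not establish that. Nor does the row say that a single UTI code is enough, since stricter UTI definitions stand beside the bare codes.

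Two further inferences are tempting. One is that the primary rate is already inflated by some multiple. Inflation depends on the full list being run, and any multiple would rest on assumed rates. The other is that combining incontinence with retention prevents the study from reporting obstructive harm. It does not: retention has its own codes and is a listed re-operation subtype, so it can be tabulated. Combining the two is a design choice, not an error.

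**Conclusion.** The point holds as a contradiction in the definition of a primary outcome. Section 7 and the row's Notes column define voiding symptoms as incontinence, retention and sling revision for retention. The row's title and code list add UTI, kidney infection and overactive bladder and, as the table reads, prolapse.

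The consequence is conditional: if the listed codes are run as the outcome, the rate would be raised and first events dated earlier by conditions outside Section 7. The direction needs no assumption beyond an any-listed-code rule. The size cannot be derived from the documents. Confidence is highest for UTI, which is in the row title, and lowest for prolapse. Rates and models are themselves conditional on data availability and quality, but that does not remove the need for one definition before data are pulled.

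**What to change.** Split the row before extraction.

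- **Outcome row:** keep only the incontinence codes, the retention/obstruction codes and sling revision for retention, with a pointer to Section 7. Sling revision for retention has no code in the present row, so bring it in from the re-operation row.
- **Covariate row:** move UTI, kidney infection, overactive bladder and prolapse here and mark them as baseline only.
- **Separate descriptive outcomes:** if post-operative infection or prolapse is of interest, report each under its own name with its own event rule.

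Tabulating incontinence and retention separately within the composite would be informative but is optional.

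The cost is an edit to one appendix row and the matching lines of the transformation code, plus one or two descriptive rows if wanted. Where the extra codes would have added events, the voiding model will have fewer, but those it has will be the ones Section 7 describes.

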Next, if the characterization of the data is sufficient for the task, we will pursue a Cox proportional hazards model analysis, with each of the outcomes assessed from the time of the surgery as a time-to-event. We will censor the time-to-event analysis with death or loss to follow-up, defined as a time period >2 years from last applicable encounter of primary care, Obstetrics & Gynecology, or Urology. The models will first be developed at each institutional separately using LASSO Cox to predict time to event for each of the outcomes of interest. We will use the variables retained in any of the individual site models, and develop a Cox model using the method described by Lu and colleagues (WebDISCO) that uses a distributed analysis approach to obtain an exact model solution without sharing case level data (only intermediate and aggregate model coefficients and matrices)¹. This method is being used to protect patient data by processing it at the local institutions and only sharing intermediate modeling statistics (aggregates) between sites.

Because bootstrapping combined with the distributed analysis method would be computationally intensive, we will utilize 10-fold cross validation across all sites for internal validation of the risk model. We assessed overall discrimination using Harrell's concordance statistic (C-statistic). To provide calibration assessments, we will also evaluate the model at fixed time points of 1 year and 2 year for each outcome using the AUC and the Estimated Calibration Index (ECI). The ECI looks at the squared difference between the predicted probability and an estimated observed probability, ranging between 0 and 100, with 0 meaning perfect calibration. Additionally, we will graphically analyze calibration by investigating the smoothed observed-to-predicted probability plot.

Target Population:All women aged 18 or greater undergoing transvaginal surgery for stress
urinary incontinence with or without mid-urethral mesh sling implantation
are eligible for inclusion in the EHR data. Determination of the appropriate
mesh exposure during surgery will be determined through administrative
CPT procedure codes, as defined in the appendix. No exclusions will be
applied based on race or ethnicity. As a separate sensitivity analysis to
reduce potential lack of outcome ascertainment, we will exclude all
patients that do not also have continuity of care within the data site,

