5. TARGET POPULATION

Inclusion criteria:

- All women aged 18 or greater undergoing transvaginal surgery for stress urinary incontinence (index surgery) with or without mesh implantation
- EHR-Based study date range 2010-2019
- Inpatient or outpatient visit

Exclusion criteria:

- No primary care, ob/gyn, or urology visits in the year prior to the surgery
- Prior pelvic organ prolapse surgery
- Prior stress urinary incontinence surgery
- Prior surgery diagnosis of a urethral diverticulum ICD-9-CM code 619.0 or any urinary-genital tract fistula (codes 599.1 and 599.2) in the 90 days prior to the index surgery.

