13. APPENDICES

Synthetic Mid-Urethral Slings for Stress Urinary Incontinence in Women Appendix: Data Collection

Category	Name	Definition, structured?	CDM?	Notes
Covariate	Age @ Procedure	Age as difference between date of surgery and date of birth	Yes- derived to remove PHI	
Outcome	Date of Death	The date on which the patient died.	Yes	Capture as date/time Lahey Comments: Captured only within institution, working on linkage to the SSI Death Index, otherwise would need chart review. Death status is more easily ascertained but not the death of death.
Inc/Excl Criteria	Surgery Indication (POP vs SUI)	Structured Codes Include Sling CPT: 57288 Include Lap sling CPT: 51992	Yes	CPT: 57288 includes retropubic midurethral slings, transobturator slings, and minislings,

Protocol 1				[15 July 2020]
				single-incision sling, adjustable sling CPT: 51992 includes laparoscopy approach.
Exposure	Mesh Implantation	Yes/No	Yes	Key Exposure
Covariate	Gender	Gender	Yes	
Covariate	Race	White, Black or African American, American Indian or Alaska Native, Asian, Native Hawaiian or Other Pacific Islander	Yes	
Covariate	Ethnicity	Hispanic or Non-Hispanic	Yes	
Covariate	Women's Health History: pregnancies, vaginal deliveries, and menopausal status ⁵²	Look for Gravida/Parity in problem list: ex: G3P3? Possible administrative codes: Grand multipara status only (not pregnant) ICD9/10- V61.5/Z64.1 Grand multiparity SNOMED- 364325004/452221000000100/ 440681000000102 # Parity LOINC- 11977-6 Unspecified menopausal and post-menopausal disorder ICD 9/10 627.9/N95.9 Premature menopause ICD9/10 256.31/E28.31 Post-menopausal bleeding ICD 9/10 627.1/N95.0	Partial, Admin Codes	May miss portion of data if admin codes only

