		 Mesh exposure and erosion (ICD9/10 629.31, 629.32/T83.711, T83.721) Urinary Retention (CPT Code 53500, ICD 9/10 788.20, 788.21/R33.0, R33.8-R33.9) Urgency of urination (ICD9/10 788.63/R39.15) Urge incontinence (ICD9/10 788.31/N39.41) Bowel injury (ICD9/10 569.83/S36) Bladder/urethral injury (ICD9/10 596.6,867.0/S37) Infection (ICD9/10 686.9,998.5,999.3,998.51,998.59/T81) Retropubic hematoma (ICD 9/10 568.81,,568.81,459.0/K66.1) Retopubic hematoma (ICD 9/10 568.81,,568.81,459.0/K66.1) Retopubic hematoma (ICD 9/10 568.81,568.81,459.0/K66.1) Bulking Injection CPT 51715, ICD 9/10 59.72/ PCS 3E0K3GC Laparoscopic Retropubic Urethropexy CPT 51990, 51992, 51999 Abdominal Retropubic Urethropexy CPT 51840,51841 Needle Bladder Neck Suspension CPT 51845 Kelly plication CPT 57220 Cystourethroplasty CPT 51800 Subtypes: Stress incontinence, female/mixed incontinence (ICD9/10 625.6,788.33/N39.46) Stress incontinence (female) (male)(ICD10 CM N39.3) 		
Outcome	Mesh Removal	 General, CPT 57287-Removal or revision of sling for stress incontinence (fascia or synthetic) ***some erosions managed surgically may have been coded by a different CPT (i.e. 57295 revise vaginal graft via vaginal approach) and not CPT 57287, which indicates a sling revision/removal. 	Yes	Possible Options: (a surgery for any kind of mid-urethral sling, urethral bulking agent, black neck pubovaginal sling (autologous or allograft), or revision for mesh exposure). Represented as a Date, allows time-to-event analysis.
Outcome	Post-Procedural Pain	?, mix of vital sign (pain score >3 of 10 on vital sign data) and likely free text. Also, diagnosis codes related to abd/pelvic pain (if prior pain free).	Some portion	Would have to exclude prior chronic pain or detect specific mention of new pain (free text). Could analyze group with no pre-surgical pain,

Protocol 1				[15 July 2020]
				otherwise probably beyond scope. Date/Time of first post- op occurrence.

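### The mesh group rests on CPT 57288, a sling code that does not state material; fascial slings have no visible vaginal or open comparator code, and the transvaginal criterion contradicts the Burch and laparoscopic comparator codes

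*Protocol*

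**What the plan says.** **Exposure.** The Synopsis (Target Population) states that "mesh exposure during surgery will be determined through administrative" CPT codes, with the appendix supplying the definition. Section 4 adds: "The key exposures will be MUS devices identified by administrative codes". In the Section 13 data collection table, the exposure row for SUI with mesh is "Admin Codes CPT 57288", with no second code and no condition on material.

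**Comparator.** Section 4 describes it as "surgery for SUI without mesh (autologous or cadaveric fascial sling or burch colposuspension or bulking agents". Section 6 gives a shorter list: autologous fascial sling and Burch, without cadaveric slings or bulking agents. The Synopsis describes the comparator as any SUI procedure without mesh and gives no route.

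**Eligibility.** Section 5 admits women "undergoing transvaginal surgery for stress urinary incontinence (index surgery) with or without mesh implantation". The inclusion row of the appendix says "Include Lap sling CPT: 51992", a laparoscopic code that the exposure table then places in the non-mesh group. The Re-Operation row labels the Burch-type codes "Abdominal Retropubic Urethropexy CPT 51840,51841".

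**The concern.** Mesh or no mesh is marked as the key exposure, and two products depend on it: the rates reported separately for the mesh and non-mesh strata, and the risk prediction model built among women who received mesh. If the code behind the mesh group also collects slings made of fascia, women without mesh sit in the denominator for erosion and in the model's training data. The comparator stratum also loses the procedure that Section 4 names first.

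The eligibility wording raises a second problem. A programmer who applies Section 5 literally and one who applies the appendix code list would build different comparator groups. One site writes the transformation code for all five and patient-level data stay local, so either reading would be repeated everywhere, and a late correction would mean rerunning every site.

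**Working it through.** There is no protocol figure to reproduce; the check is a comparison of code lists, followed by illustrative arithmetic.

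**Step 1: does 57288 identify material?** The Synopsis site description and the CPT list at the end of Section 13 both call it only a sling operation for stress incontinence. The Mesh Removal row describes the companion code 57287 as "Removal or revision of sling for stress incontinence (fascia or synthetic", so that code spans both materials. Against this, the note beside 57288 in the inclusion row lists only midurethral types (retropubic, transobturator, mini, single-incision, adjustable). The protocol never says that fascial slings are coded 57288; that is inferred from the generic label, the wording of 57287 and the lack of another code.

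**Step 2: which comparators have a code, and do they meet Section 5?**

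| Non-mesh procedure | Code in non-mesh row | Route as labelled in the appendix | Fits a transvaginal criterion? |
|---|---|---|---|
| Fascial sling, vaginal or open | none visible | – | cannot be identified |
| Laparoscopic suspension or sling | 51990, 51992 | laparoscopic | no |
| Burch type | 51840, 51841 | abdominal | no |
| Vesical neck suspension | 51845 | abdominovaginal; elsewhere a needle suspension | unclear |
| Bulking injection | 51715 | neither abdominal nor laparoscopic | not stated, not clearly excluded |
| Kelly plication | 57220 | none given | not excluded |

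A pubovaginal sling procedure code (59.79) appears in the reference list at the end of Section 13 but not in the exposure row.

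**Step 3: does any stated rule move a fascial sling out of the mesh group?** Section 6 applies string matching to extract the surgical approach, plus hand-cut and tensioned status; material is not among the targets. Section 8.1 draws notes only for cases already identified as mesh. Chart review of 50 to 100 cases per site validates data elements but carries no reclassification rule. Sling brand is recorded as free text outside the common data model.

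**Step 4: scale.** Three sites give multi-year counts of 57288: 6,106 + 5,413 + 887 = 12,406. Let f be the fascial share. The protocol does not give it, so I assume 2% to 15%.

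- Women in the mesh group without mesh = f × 12,406: 0.02 × 12,406 ≈ 248; 0.15 × 12,406 ≈ 1,861.
- Observed erosion risk = (1 − f) × p, if women without mesh have no erosion event. With p = 1.6% (the New York registry figure in Section 1.1): 0.98 × 1.6% = 1.57%; 0.85 × 1.6% = 1.36%.

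The formula does not carry over to mesh removal, because 57287 would also count removal of a fascial sling.

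**The case against.** A reader might infer that neither named comparator can enter the non-mesh group. The documents do not support that. Section 4 names bulking agents, which have code 51715, and Kelly plication and possibly 51845 can also enter. Nor is Burch shown to be lost: Section 4 names it, the appendix codes it, and the Synopsis defines the comparator without a route. Section 5 contradicts those passages; it does not settle the matter against them.

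A reader might also take it as stated that fascial slings are counted as mesh. The inclusion-row note, which lists only midurethral types, tells against certainty. The non-mesh row also ends mid-phrase in the text available for this review, so a further code could have followed.

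Other safeguards deserve credit. Section 4 refers to device implantation data as well as administrative codes. The appendix has a separate yes/no mesh field. Section 11 plans analysis by approach and implant type. A fascial sling should match none of the four approach categories. Chart review might expose the problem. Listing 51992 both as a cohort-entry code and as non-mesh is not in itself a contradiction, since the cohort includes women without mesh.

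Finally, Sections 4 and 9.1 rule out a direct comparison of the groups, the counts precede the Section 5 exclusions, and the fascial share is assumed.

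These points limit the claim but do not remove it. None of the safeguards is tied to a rule assigning a fascial sling to the non-mesh group, and the eligibility conflict is on the face of the text.

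**Conclusion.** The point holds in a limited form. The mesh group is defined by one code whose label does not state material. A fascial sling, named as a comparator in two sections, has no visible vaginal or open code in the non-mesh row, so it is either counted as mesh or not captured; which of the two rests on the inference about 57288. Separately, the transvaginal criterion contradicts the Burch and laparoscopic comparator codes and the route-free Synopsis wording, and Sections 4 and 6 differ on bulking agents.

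The size cannot be determined from the protocol. Under the assumed 2% to 15% share the dilution of an erosion rate is modest, 0.03 to 0.24 percentage points on 1.6%. The comparator's composition may change more, since it could lack fascial slings altogether and, depending on which passage is followed, Burch and laparoscopic procedures. The stratified rates and the mesh-only model carry the consequences, so the definition should be settled before extraction.

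**What to change.** 1. Add sling-material terms (synthetic; autologous, cadaveric, fascia) to the Section 6 string match on the operative notes already extracted for 57288 cases. Assign mesh or non-mesh from the result.
2. Report cases whose material cannot be resolved as a separate group and leave them out of the mesh model.
3. State how 51992 is assigned. Checking its material would need notes that are not now extracted, because those cases are coded non-mesh.
4. Limit the transvaginal criterion in Section 5 to the mesh group, so that it agrees with the comparator code list.
5. Use one comparator list in Section 4, Section 6 and the appendix, including a decision on bulking agents and cadaveric slings.

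The cost is some extra search terms and their validation in notes already being annotated, plus wording changes. The downside is that some unresolved cases are set aside. Only step 3 could need additional notes.
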